1.2. Pridopidine Therapeutic Rationale

Target engagement in humans and prior evidence of clinical efficacy

The proposed dose for the HEALEY ALS Platform Trial Regimen D is 45 mg BID. At this dose, pridopidine shows near to complete occupancy of the S1R in human brains (>90% S1R occupancy) with negligible (~3%) binding to the D2/D3Rs, suggesting its dominant pharmacological effect at this dosage is mediated via the S1R.

The S1R regulates cellular signaling pathways that are commonly impaired in various neurodegenerative disorders, such as calcium signaling, mitochondrial function, and spine loss. Loss of function (LOF) mutations in S1Rs are associated with juvenile ALS and missense mutations with adult-onset ALS. LOF mutations are also associated with distal hereditary motor neuronopathies (dHMN). Pridopidine, via activation of the S1R, exerts neuroprotective properties in numerous preclinical models including ALS, HD, PD and AD and may, therefore, have therapeutic effects in ALS.

The PRIDE-HD study was a 52-week, double-blind, phase 2 trial to evaluate the efficacy and safety of pridopidine in participants with HD. Post-hoc analysis of data from PRIDE-HD demonstrated pridopidine 45 mg BID significantly maintained total functional capacity (TFC) in early HD participants at 52 weeks. (Reilmann, Olanow, et al. 2019)

TFC is the most widely accepted and validated tool for assessing disease stage and correlates with advancing pathology and disease progression (Shoulson and Fahn 1979; Marder et al. 2000). Decline in TFC parallels the decline in other measures, including motor, cognitive, neuropsychiatric, and functional assessments (Tabrizi et al. 2013; 2012; Dorsey et al. 2013). It has been used as an endpoint in more than ten other clinical trials of drugs seeking to demonstrate impact on HD progression, none of which were positive.

Pridopidine 45 mg BID also demonstrates a good safety profile. An integrated analysis of adverse events (AEs) was performed using a large safety database (over 1,300 participants) generated from 22 clinical studies with pridopidine. This analysis shows that the AE profile of pridopidine 45 mg BID is comparable to placebo. These results further suggest that there is no increased risk of psychiatric symptoms or cardiac toxicity with pridopidine 45 mg BID.

Taken together, compelling preclinical data and clinical data demonstrate that pridopidine 45 mg BID has:

- (1) Robust and selective human in-vivo S1R target engagement (PET imaging)
- (2) Neuroprotective effects in numerous preclinical models of neurodegeneration, including ALS, HD, PD and AD
- (3) Significant effect on maintaining total functional capacity at 52 weeks in early HD participants in comparison to placebo in a double-blind study, and
- (4) A favorable safety and tolerability profile

These, and the genetic link between the S1R and ALS, justify a study to test the clinical benefits of pridopidine in ALS.

Dosing Regimen

The proposed dose to be tested in the planned study is 45 mg twice daily (BID), taken in the morning and in the early afternoon (approximately 7 to 10 hours after the morning dose).

There will be a titration period leading up to the proposed dose whereby participants will initiate pridopidine at 45mg once daily (QD) and then increase to 45mg BID after 2 weeks.

2 STUDY OBJECTIVES AND ENDPOINTS

Primary Efficacy Objective:

- To evaluate the efficacy of pridopidine as compared to placebo on ALS disease progression.

Secondary Efficacy Objective:

- To evaluate the effect of pridopidine on selected secondary measures of disease progression, including survival.

Safety Objective:

- To evaluate the safety of pridopidine in ALS patients.

Exploratory Efficacy Objective:

- To evaluate the effect of pridopidine on selected biomarkers and endpoints.

Primary Efficacy Endpoint:

Change in disease severity as measured by the ALS Functional Rating Scale-Revised (ALSFRS-R) total score using a Bayesian repeated measures model that accounts for loss to follow-up due to mortality.

Secondary Efficacy Endpoints:

- Change in bulbar function as measured by the ALSFRS-R bulbar subdomain (Q1-Q3) score among participants with bulbar dysfunction at baseline.
- Change in bulbar function as measured by the ALSFRS-R bulbar subdomain (Q1-Q3) score among all randomized participants.
- Change in speech as measured by the ALSFRS-R speech domain score (Q1) among all randomized participants.
- Change in respiratory function as measured by slow vital capacity (SVC).
- Change in bulbar function as measured by the ALSFRS-R bulbar subdomain (Q1-Q3) score among participants with rapid pre-baseline progression.
- Time to first evidence of bulbar dysfunction.
- Change in muscle strength as measured isometrically using hand-held dynamometry (HHD) and grip strength.
- Survival.

Safety Endpoints:

- Treatment-emergent adverse and serious adverse events.
- Changes in laboratory values and treatment-emergent and clinically significant laboratory abnormalities.
- Changes in ECG parameters and treatment-emergent and clinically significant ECG abnormalities.
- Treatment-emergent suicidal ideation and suicidal behavior.

Exploratory Efficacy Endpoints:

HEALEY ALS Platform Trial
Regimen-Specific Appendix D, Pridopidine
Version 2.0, 15-July-2021
CONFIDENTIAL

- Changes in quantitative voice characteristics.
- Changes in biofluid biomarkers of neurodegeneration.
- Changes in patient reported outcomes (e.g. CNS-BFS, CNS-LS).
- Change in respiratory function as assessed by home spirometry.

3 RSA DESIGN

This study is a multi-center, randomized, placebo-controlled trial, testing active dose of pridopidine (45mg BID), given orally daily versus placebo. Participants will be randomized 3:1 active: placebo.

The study will consist of a screening/baseline visit, a 2-week double-blind, placebo-controlled up-titration period, a 22-week double-blind, full-dose, placebo-controlled treatment period, and a 28-day safety follow-up period (after the last dose of IP) for those participants who do not enter the Open Label Extension (OLE) period of the study.

After signing informed consent, participants will undergo screening assessments to determine eligibility and eligible participants will be randomly assigned in a 3:1 ratio to 1 of 2 study intervention groups:

- Treatment Arm 1 (active): pridopidine 45 mg orally (PO), BID (total daily dose of 90 mg after two week up-titration period at 45mg PO, QD)
- Treatment Arm 2 (control): matching placebo, PO BID

During the 2 week up-titration period (starting on Day 1), all participants will self-administer 1 capsule of study intervention PO once daily (QD) in the morning. In the full-dose treatment period (starting on Day 14) study intervention will be taken BID, in the morning and in the afternoon (approximately 7-10 hours apart). Participants who complete all scheduled visits will have the option of participating in the OLE period of the study.

Throughout the study, participants will be assessed through on-site clinic visits and telephone calls, as specified in the Schedule of Activities (SoA) table.

For participants who complete all scheduled visits, their final visit will be the Follow-Up Safety Call (28 days after the Week 24 clinic visit), unless participants continue on in the OLE. Participants who discontinue study intervention early will be encouraged to complete all other visits as scheduled for the full course of the study per ITT. For participants who withdraw early from the placebo-controlled period, an in-person Early Termination Visit and a Follow-up Safety Call should be conducted. At the Early Termination Visit the same procedures as described for the Week 24 visit should be conducted. At the Follow-up Safety Call, information on clinical status should be collected.

Participants who complete the full study regimen (24 weeks) will have the option to enroll into the OLE period of the study and receive pridopidine 45 mg orally BID (total daily dose of 90 mg), following a 2 week up-titration period at QD.

3.1 Scientific Rationale for RSA Design

This RSA is designed to correspond with the design of the Master Protocol and the goals of the Platform Trial.

3.2 End of Participation Definition

HEALEY ALS Platform Trial
Regimen-Specific Appendix D, Pridopidine
Version 2.0, 15-July-2021
CONFIDENTIAL

A participant is considered to have ended his or her participation in the placebo-controlled period of the Regimen if they:

- Complete planned placebo-controlled period visits, as described in the SOA, including participants on or off study drug
- Early terminate from the study and complete the Early Termination Visit and Follow-Up Phone call as described in Section 6.1.11
- Withdraw consent to continue participation in the study or are lost to follow-up

3.3 End of Regimen Definition

The end of the placebo-controlled period in a Regimen occurs when all randomized participants have completed their participation in the placebo-controlled period as defined in section 3.2.

The end of the OLE period in a Regimen occurs when all participants who initiated open-label IP in the OLE period have completed their participation in the OLE period as defined in section 3.2.

4 RSA ENROLLMENT

4.1 Number of Study Participants

Approximately one hundred-sixty participants will be randomized for this Regimen.

4.2 Inclusion and Exclusion Criteria

To be randomized to a Regimen, participants must meet the Master Protocol eligibility criteria. In addition, participants meeting all of the following inclusion and exclusion criteria at the Regimen Screening Visit will be allowed to enroll in this Regimen:

4.2.1 RSA Inclusion Criteria

There are no additional RSA Inclusion Criteria from those described in the Master Protocol.

4.2.2 RSA Exclusion Criteria

1. Participants with a confirmed prolonged Fridericia-corrected QT (QTcF) interval (defined as a QTcF interval of >450 ms for men and >470 ms for women).
2. Participants with clinically significant heart disease, clinically significant history of arrhythmia, symptomatic or uncontrolled atrial fibrillation despite treatment, or asymptomatic sustained ventricular tachycardia, or presence of left bundle branch block.
3. Participants with known history of long QT syndrome or a first degree relative with this condition.
4. Participants using prohibited medications within the 4 weeks prior to the Regimen Specific Screening Visit, as detailed in section 5.9.
5. Participants using the following medications at the time of the Regimen Specific Screening Visit:
 - a. Nuedexta – at a dosage higher than 20 mg dextromethorphan + 10 mg quinidine BID
 - b. Citalopram – at a dosage higher than 20 mg/day
 - c. Escitalopram – at a dosage higher than 10 mg/day
6. Participants with a known allergy to any ingredient of the study intervention (pridopidine, silicified microcrystalline cellulose, and magnesium stearate).

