- ⁹ In addition to study visits outlined in the SOA, participants will be asked to complete twice weekly voice recordings at home.
- ¹⁰ Drug will only be dispensed at this visit if the participant continues in the OLE.
- ¹¹ Participants will only have a Follow-Up Safety Call at this time if they *do not* continue on in the OLE. Participants who continue into OLE will have a Follow-Up Safety Call after their last dose of IP during the OLE period.
- ¹² Vital status, defined as a determination of date of death or death equivalent or date last known alive, will be determined for each randomized participant at the end of the placebo-controlled portion of their follow-up (generally the Week 24 Visit, as indicated). If at that time the participant is alive, his or her vital status should be determined again at the time of the last participant's last visit (LPLV) of the placebo-controlled portion of a given regimen. We may also ascertain vital status at later time points by using publicly available data sources as described in section 8.15 of the Master Protocol.
- ¹³ If the CSF collection is unable to be performed for logistical reasons, such as scheduling, at the Week 16 Visit, it may be performed at the Week 24 Visit.
- ¹⁴ If a participant's visit occurs in the morning, the participant should be instructed that the morning dose of study medication should not be taken, and the morning dose should be administered in-clinic 1-2 hours prior to the **POST-DOSE** ECG. If a participant's visit occurs in the afternoon, the participant should be instructed to take the morning dose immediately upon waking in the morning, and the second dose should be administered in-clinic 1-2 hours prior to the **POST-DOSE** ECG.
- ¹⁵ At the regimen-specific Screening visit (and Week 24 for participants enrolling in OLE), QTcF will be determined by the mean of three, 10-second recordings of a 12-Lead ECG (performed at least 1 minute a part) **BEFORE** IP administration. For participants on Nuedexta, the Nuedexta dose should be taken within 6 hours **BEFORE** the ECG, refer to the MOP for additional guidelines.
- ¹⁶ At Baseline and Week 4 (and Week 24 for participants enrolling in OLE) QTcF will be determined by a single 10-second 12-lead ECG, 1-2 hours **AFTER** IP administration. If stopping or monitoring rules are met, refer to Section 4.4. For participants on Nuedexta, the Nuedexta dose should be taken within 6 hours **BEFORE** the ECG, refer to the MOP for additional guidelines.

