1.1.2. Overview of the Clinical Development Program

To date, 1,334 participants have received at least one dose of pridopidine across numerous clinical trials. Of these 1,334 participants, the large majority (74%, 987 participants) were exposed to a daily pridopidine dose of 45 mg BID, with the remaining participants exposed to a daily dose ranging between 10 mg to 112.5 mg BID. On a cumulative exposure level, approximately 1,300 participant-years of exposure to pridopidine have been accumulated. The majority of participants exposed to pridopidine to date have been participants with HD.

Clinical Pharmacology

To date, 13 studies have been conducted investigating the pharmacokinetics of pridopidine. Seven studies were used for the development of the population pharmacokinetic model (PPK), including phase 1 studies: ACR16C012, ACR16C013, ACR16C016, and ACR16C018; phase 2 studies: ACR16C009 (HART) and TV7820-CNS-20002 (PRIDE-HD); and a phase 3 study ACR16C008 (MermaiHD). Pridopidine steady-state pharmacokinetics are described by a 2-compartment linear model with first-order absorption. Of the covariates studied, only weight and participant CYP2D6 metabolizer status influenced apparent clearance.

Pridopidine has a relatively fast and almost complete absorption after oral administration, with individual C_{max} occurring between 0.5 and 4 hours after dosing (the median time to maximum concentration in plasma [T_{max}] is 1.25 to 2 hours). Food intake has no impact on the extent of absorption of pridopidine. After absorption, pridopidine is eliminated partly by urinary excretion and partly by hepatic metabolism (primarily via the CYP2D6 pathway), with a mean half-life (t_{1/2}) of approximately 10 hours at steady-state. In extensive metabolizers (EMs), pridopidine is metabolized by CYP2D6 to 1 main metabolite (TV-45065). Conversely, poor metabolizers (PMs) depend on renal excretion as their main elimination pathway.

Prior to reaching steady-state pharmacokinetics, pridopidine is metabolized by CYP2D6 to one main inactive metabolite (TV-45065). However, since CYP2D6 undergoes auto-inhibition; the fraction of pridopidine that is metabolized by CYP2D6 decreases with multiple doses, renal elimination becomes a more important elimination pathway, and the fraction excreted unchanged increases. Steady state is reached after approximately 10 days.

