Mild renal impairment (defined as glomerular filtration rate (GFR) of 60-89 mL/min/1.73 m²) did not affect the steady-state pharmacokinetics of 45 mg of pridopidine once daily (QD). Participants with moderate renal impairment (defined as GFR of 30-59 mL/min/1.73 m²) had 1.68-fold higher AUC and 1.26-fold higher C_{max} values than matching healthy participants at steady state.

Studies in participants with hepatic impairment have not been performed, but PMs are expected to represent a worst-case scenario for hepatic impairment with minimal increase in pridopidine exposure (C_{max} or AUC). In the PRIDE-HD study, no dose adjustment was implemented for PM participants, and this population was administered up to 112.5 mg BID with no difference in the safety profile. Therefore, no dose adjustments are proposed for participants with hepatic impairment.

The potential for drug-drug interactions with pridopidine is predicted to be very low, with the exception of co-administration of pridopidine with CYP2D6 substrates. Pridopidine is a CYP2D6 inhibitor, and increased exposures of co-administered CYP2D6 substrates are anticipated. Caution should be exercised with medications that are mainly eliminated via a CYP2D6-dependent pathway and have a narrow therapeutic index and/or have a concern related to QT prolongation.

Clinical Safety

HEALEY ALS Platform Trial
Regimen-Specific Appendix D, Pridopidine
Version 2.0, 15-July-2021
CONFIDENTIAL

All AEs across all clinical studies (22 studies) were combined into an integrated safety database. Since the majority of participants exposed to pridopidine to date have been on the 45 mg BID dosage regimen (74% of participants, 84% of the cumulative participant-years of exposure), AEs are presented for the following two groups:

- (1) Pridopidine 45 mg BID - all participants who received pridopidine 45 mg BID at least one time but did not receive a dose higher than 45 mg BID
- (2) Placebo - all participants in pridopidine clinical studies who did not receive a single dose of pridopidine

Due to the considerably different number of participant-years (PY) of exposure between the groups, an analysis of AE reporting rates corrected for participant-years of exposure was performed in addition to AE incidence.

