In accordance with the ICH E14 Guideline, Clinical Evaluation of QT/QTc Interval Prolongation and Proarrhythmic Potential for Non-Antiarrhythmic Drugs, the safety database was analyzed for rates of clinical events indicating a proarrhythmic potential, and the rates observed in treated and control participants were compared. An analysis of the full safety database that includes all participants treated with at least one dose of pridopidine found no events of torsade de pointes following treatment with pridopidine at doses of up to 112.5 mg BID. One case of mild ventricular arrhythmia was reported.

Exposure-response analysis of QT Prolongation

The PRIDE-HD trial incorporated extensive electrocardiogram (ECG) monitoring and a pharmacokinetic (PK) sampling schedule that captured peak plasma concentrations over 52 weeks.

ECGs and PK data from the PRIDE-HD study resulted in a comprehensive exposure-response analysis, including data from >400 HD participants, treated with 5 doses of pridopidine (including placebo), for up to 1 year.

A concentration-dependent effect of pridopidine on the QTcF interval was observed with a slope of 0.012 ms per ng/mL (90% CI: 0.0109 to 0.0127 ms per ng/mL).

At the proposed dose of 45 mg BID, the predicted QT effect ($\Delta\Delta\text{QTcF}$) in participants with HD was 6.6 ms (with an upper bound of the 90% confidence interval of 8 ms), which is not clinically meaningful.

In summary, in the PRIDE-HD study, QT prolongation was found to be an adverse drug reaction associated with the use of pridopidine. At 45 mg BID, the dose to be tested in the ALS trial, there is no clinical significance of QT prolongation.

Table 1 Clinical Events indicating Proarrhythmic Potential across Entire Safety Database

	Placebo		Pridopidine 45 mg BID	
	Incidence N=338	Rate PY = 148.8	Incidence N=981	Rate PY = 1091
QT Prolongation	2 (0.6%)	Rate = 0.013	5 (0.5%)	Rate = 0.005
Torsade de pointes	0	0	0	0
Sudden death	0	0	0	0
Ventricular arrhythmias	0	0	1 (0.1%)	Rate=0.0009
Ventricular tachycardia	0	0	0	0
Ventricular fibrillation	0	0	0	0
Ventricular flutter	0	0	0	0
Syncope	1 (0.3%)	Rate =0.007	16 (1.6%)	Rate =0.016

PY= participant year; rate is events/participant year

Table 2 Clinical Events indicating Proarrhythmic Potential in Placebo-Controlled Period of the PRIDE-HD Study

	PRIDE-HD					
	Placebo N=82	45 mg BID N=81	67.5 mg BID N=82	90 mg BID N=81	112.5 mg BID N=82	All Pridopidine N=327
QT Prolongation	0	2 (2.5%)	0	1 (1.2%)	2 (2.5%)	5 (1.5%)

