5.10 Prohibited Medications

Excluded Medications:

Class	Drugs
Antipsychotics	Clozapine, haloperidol, mesoridazine, thioridazine, pimozide, chlorpromazine, perphenazine, risperidone, zuclopenthixol, and sulpiride.
Antiarrhythmic	Disopyramide, procainamide, flecainide, propafenone, amiodarone, dofetilide, ibutilide, and sotalol
Others	Astemizole, terfenadine, azithromycin, erythromycin, moxifloxacin, pentamidine, sparfloxacin, clarithromycin, chloroquine, halofantrine, bepridil, cisapride, domperidone, droperidol, levomethadyl, sevoflurane, anagrelide, budipine, fluconazole, levofloxacin, lidoflazine, ondansetron, probucol, terodiline, vandetanib, tramadol, tamoxifen, atomoxetine, tolterodine

Participants who use the above medications while enrolled in Regimen D of the HEALEY ALS Platform Trial increase their risk of QT prolongation and torsades. If participants inadvertently use these medications while they are on IP, the Medical Monitor should be notified and a single 12-lead ECG should be collected within 3-14 days of initiating the new prohibited co-medication, or higher dose, to test for QTcF prolongation meeting the Monitoring or Stopping Rules.

If there is a clinical indication for any medication specifically prohibited during the study, the Medical Monitor will be notified and engaged in consultation as to how to address.

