5.11 Pridopidine Known Potential Risks and Benefits

5.11.1 Known Potential Risks

QT prolongation:

In the PRIDE-HD trial of 408 participants, the cardiac effects of pridopidine were evaluated in people with HD at doses up to 112.5 mg BID for 52 weeks. Although low, there was a higher overall incidence of AE-reports of QT prolongation in pridopidine-treated participants compared to placebo-treated participants: 1.5% in pridopidine-treated participants vs 0% in placebo-treated participants. However, there was no evidence of a dose response in QT-related AEs (QT prolongation AEs: 0 in placebo, 2 in 45 mg BID, 0 in 67.5 mg BID, 1 in 90 mg BID and 2 in 112.5 mg BID; total 5/327=1.5%). Using the PRIDE-HD data, a cardiac exposure-response model was developed utilizing ECG data paired with PK samples collected for up to a year. Only ECGs that were paired with PK samples (n=3071) were used to develop the cardiac exposure-response model, which was based on 2753 ECGs from pridopidine-treated participants and 763 from placebo-treated participants.

A concentration-dependent effect of pridopidine on the QTcF interval was observed in this study, with a slope of 0.012 ms per ng/mL (90% CI: 0.0109 to 0.0127 ms per ng/mL).

At 45 mg BID, the predicted QT effect ($\Delta\Delta\text{QTcF}$) in participants with HD was 6.6 ms (with an upper bound of the 90% CI 8 ms), which is not clinically meaningful. Pridopidine 45 mg BID is the dose to be tested in the HEALEY ALS Platform Trial. Although this was not a clinically meaningful QT effect, as there is no prior experience with pridopidine in the ALS patient population, we plan to include additional safety monitoring and risk mitigation measures.

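### In the RSA and R-SAP, the dose caps on Nuedexta, citalopram and escitalopram apply only at screening, and the on-study ECG trigger as worded does not reach these drugs

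*Protocol*

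**What the plan says.** Criterion 5 in Protocol 4.2.2 excludes "Participants using the following medications at the time of the Regimen Specific Screening Visit" above three limits: Nuedexta 20 mg dextromethorphan plus 10 mg quinidine BID, citalopram 20 mg/day and escitalopram 10 mg/day. SAP 2.3 summarises the criterion with the same time point. Drugs barred outright are handled separately, in criterion 4 and the table in 5.10.

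Section 5.10 sets the on-study rule for the drugs in that table. Its ECG action is that "a single 12-lead ECG should be collected within 3-14 days of initiating the new prohibited co-medication, or higher dose". That action, like the report to the Medical Monitor, depends on use of a listed drug: "If participants inadvertently use these medications while they are on IP, the Medical Monitor should be notified". The table names none of the three criterion 5 drugs.

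Three other provisions bear on the point:

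- Section 4.4 applies QT stopping and monitoring rules to every participant. On-treatment ECGs are scheduled at Baseline (post-dose), Week 4 and Week 24.
- Section 1.1.2 describes pridopidine as a CYP2D6 inhibitor and says "Caution should be exercised with medications that are mainly eliminated via a CYP2D6-dependent pathway", where these also have a narrow therapeutic index or a QT concern. It names no drug and attaches no action.
- The Schedule of Activities footnotes fix when Nuedexta is taken relative to an ECG and tell sites to "refer to the MOP for additional guidelines". They give no dose limit.

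**The concern.** A dose judged too high for entry should prompt a check if it is reached while the participant is on study drug. As the RSA is worded, it does not. The documents give no reason for criterion 5. I assume QT risk, because 5.10 is about QT prolongation and torsades and because Nuedexta dosing is timed to the ECGs.

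Section 1.1.2 says the predicted QT effect at 45 mg BID "in participants with HD was 6.6 ms (with an upper bound of the 90% confidence interval of 8 ms), which is not clinically meaningful". That prediction comes from Huntington disease and is not given for use together with these drugs above their caps. Section 5.11.1 itself says that "as there is no prior experience with pridopidine in the ALS patient population, we plan to include additional safety monitoring".

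Use of at least one of the three drugs is expected. SAP 6.5.2 and 6.5.3 adjust for baseline Nuedexta use, and SAP 4.1 lists an endpoint among participants taking it at baseline.

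**Working it through.** **Does any rule carry the caps forward?**

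- *Criterion 5 and SAP 2.3:* both are tied to the Regimen Specific Screening Visit.
- *Section 5.10, trigger sentence:* its condition is use of the listed drugs. The reference to a higher dose at the end of "a single 12-lead ECG should be collected within 3-14 days of initiating the new prohibited co-medication, or higher dose" follows the words about a prohibited co-medication, so grammatically it stays with the table.
- *Section 5.10, closing sentence:* Medical Monitor consultation is for drugs specifically prohibited during the study. The three drugs are permitted below their caps and are not listed.
- *OLE entry:* 6.2 requires completion on drug, and 4.4 and 6.1.8 require a Week 24 mean QTcF within the sex-specific limits. The caps are not repeated.

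**How long could an increase wait for an ECG?**

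Inputs from the Schedule of Activities and 6.2: Week 4 is Day 28 ± 7 (21-35) and Week 24 is Day 168 ± 7 (161-175). OLE Week 4 is Day 28 ± 7, and OLE Week 24 is printed as Day 196 ± 14 (182-210). The comparison is the 3-14 days in 5.10.

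| Interval to next scheduled ECG | Nominal (days) | Shortest | Longest |
|---|---|---|---|
| Day 1 to Week 4 | 28 − 1 = 27 | 21 − 1 = 20 | 35 − 1 = 34 |
| Week 4 to Week 24 | 168 − 28 = 140 | 161 − 35 = 126 | 175 − 21 = 154 |
| OLE Week 4 to OLE Week 24, as printed | 196 − 28 = 168 | 182 − 35 = 147 | 210 − 21 = 189 |
| Same, if Week 24 means Day 168 ± 14 (154-182) | 168 − 28 = 140 | 154 − 35 = 119 | 182 − 21 = 161 |

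The last two rows are both shown because the printed Day 196 is 196/7 = 28 weeks, while 24 weeks is 24 × 7 = 168 days and OLE Week 20 is correctly Day 140. Keeping the ± 14 window around Day 168 is an assumption.

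For an increase just after the Week 4 ECG, the shortest wait exceeds the longest 5.10 interval by 126 − 14 = 112 days. For an increase on a later day d, the nominal wait is 168 − d, which exceeds 14 days whenever d < 154. On nominal days that is 154 − 28 = 126 of the 140 days in the interval, or 90%. If increases fell evenly across it (an assumption), the mean wait would be 140/2 = 70 days.

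Medication reviews at Weeks 8, 12, 16 and 20 fall inside this gap and could reveal an increase. The RSA attaches no ECG or notice to that discovery.

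**What would the next ECG capture?**

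For participants not entering the OLE, the Week 24 ECG is pre-dose only (6.1.8), whereas 1.1.2 puts "the median time to maximum concentration in plasma" at 1.25 to 2 hours. OLE entrants have a pre-dose triplicate and an ECG 1-2 hours after dosing. Section 4.4 then resets their QTcF baseline to that triplicate, so any QT effect of an earlier increase enters the new baseline and weakens the later test of change from baseline. The absolute limits are unaffected. ECGs at OLE Week 24 and the final OLE visit are again pre-dose (6.2.7).

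**The case against.** The strongest reply is that the RSA is not the whole rulebook. Concomitant medication review is a Master Protocol activity, and sites are repeatedly sent to the MOP on Nuedexta, so either document may hold an on-study limit. This stands as a limit on the conclusion. However, the stated MOP referrals on Nuedexta concern its timing around ECGs. The ECG flow figures in 4.4 were also not legible in the copy read, though the text around them contains no dose cap.

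A second reply is that the reference to a higher dose in 5.10 must mean these drugs, since a dose increase means little for drugs barred at any dose and only the criterion 5 drugs carry limits. Coverage was probably intended. That is a reason to correct the wording, because a site should not have to infer a safety trigger.

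Third, everyone is monitored, the predicted effect is small, and 1.1.2 reports no torsade de pointes at doses up to 112.5 mg BID. All true, but QT rules act only on an ECG that has been taken.

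Fourth, a pre-dose ECG is not drug-free. The steady-state half-life is about 10 hours, afternoon attenders have taken their morning dose, and Nuedexta must be taken within 6 hours beforehand. This fairly softens the pre-dose point, as the OLE entry ECGs soften the point about OLE entry. Neither shortens the wait. The 140 days is a worst case, but on nominal days 90% of the Week 4 to Week 24 interval still gives a wait longer than 14 days.

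**Conclusion.** The concern holds on the RSA and R-SAP. The three caps end at screening, and the notice and 3-14 day ECG in 5.10 do not, as worded, apply to these drugs. It is a gap in the trigger, not an absence of QT monitoring. At its widest in the double-blind period the wait for a scheduled ECG is nominally 140 days (126-154). In the OLE it is 140 or 168 days, depending on which day OLE Week 24 is meant to be.

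The conclusion assumes that QT risk is why criterion 5 exists, and that neither the Master Protocol nor the MOP closes the gap. The documents do not say how many participants take these drugs or might exceed a cap, so the number affected cannot be estimated. Efficacy inference is not touched. The change is worth making because it is a cheap gain in participant safety; confidence is medium because of the documents not seen.

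**What to change.** Add a restricted-dose line to Protocol 5.10, for example:

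*Nuedexta above 20 mg/10 mg BID, citalopram above 20 mg/day, or escitalopram above 10 mg/day: if started at or raised to such a dose while on IP, including in the OLE, inform the Medical Monitor and obtain a single 12-lead ECG within 3-14 days.*

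This also settles what the reference to a higher dose covers. If the Master Protocol or MOP already contains an equivalent rule, cross-refer to it from 5.10 instead. The same amendment can correct criterion 4, which points to 5.9 (Overdose) for the prohibited list that sits in 5.10.

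The cost is a wording amendment, a site memo and a few unscheduled ECGs under a procedure that already exists. Eligibility, dosing and analysis stay as they are.
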